For this menthol / nicotine reinforcement study, the Test Sessions will be conducted after an Adaptation Session is completed where subjects will learn to use the e-cigarette for delivering the menthol or control (tobacco) flavor. A short e-cigarette questionnaire will also be administered during the Adaptation Session. Then, the nicotine Test Sessions will be performed following overnight abstinence from tobacco. Smokers will be assigned a random sequence of three different e-cigarette conditions (low menthol (0.5% or 5 mg/mL) plus tobacco flavor, high dose menthol (3.5% or 35 mg/mL) plus tobacco flavor or tobacco flavor alone for each of the three Test Sessions (a different menthol condition for each session). The concentration of tobacco flavor will be identical across all conditions. The amount of menthol in high dose condition is the same as those found in commercially available mentholated e-cigarette solutions (AmericaneLiquidStore™). The low dose menthol solution contains menthol that is minimally perceptible by smokers and is in the range of e-cigarette solutions targeting smokers with a preference for low menthol impact in the e-cigarette vapor. In each Test Session, smokers will receive a random order of one intravenous delivery of saline, and two intravenous deliveries of nicotine (3.6 mcg/kg and 7 mcg/kg or 0.25 mg/70 kg and 0.5 mg/70kg), just after the menthol or control flavor is delivered via the e-cigarette. The intravenous dose deliveries will be one hour apart to provide sufficient time for the nicotine and menthol effects to wear off. The nicotine infusion sessions will be at least 24 hours apart to minimize carryover nicotine effects. The main outcome measure will be subjective drug effects as measured with the Drug Effects Questionnaire (DEQ). Other outcomes include cardiovascular measures, cognitive performance, and self-report measures of nicotine withdrawal. Cardiovascular measures include heart rate, systolic and diastolic blood pressure. Cognitive performance will be assessed with the Stroop test, mathematical processing test (MPT), and continuous performance test (CPT). Nicotine withdrawal measures will be measured with the Nicotine Withdrawal Symptom Checklist (NWSC) and the Brief Questionnaire on Smoking Urges (BQSU).

B. Dose Finding Study

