- Heart rate and blood pressure: Heart rate and blood pressure readings will be taken at screening, and during each test session to measure nicotine's effect on these parameters

b) Biochemical:

- Serum estradiol and progesterone analysis (females only): Serum estradiol and progesterone levels will be measured before each test session, and will be used as covariates in our analysis, since female sex hormones may contribute to sex differences in nicotine responses (Lynch *et al*, 2010).
- Plasma cotinine and 3-hydroxycotinine (3HC): Plasma cotinine and 3-hydroxycotinine levels will be measured from blood obtained during the three Test Sessions to determine the nicotine metabolite ratio (NMR). The NMR is the ratio of 3HC, the main metabolite of cotinine, to cotinine and reflects the activity of cytochrome P450 (CYP) 2A6 and thus, the rate of nicotine clearance (Dempsey *et al*, 2004). NMR has been shown to be stable in smokers during ad-lib and reduced smoking (Mooney *et al*, 2008). Plasma samples for 3HC will be obtained at baseline, and the NMR will be included as a covariate in our analyses.

[Type text]

[Type text]

Plasma nicotine: Plasma nicotine levels will be measured from blood that was obtained prior to the first experimental vaping session on each test day to characterize the subject's smoking status.

- Urinary cotinine levels: A semi-quantitative rapid urine level of cotinine will be obtained at screening to confirm smoking status at study entry.
- Urine menthol glucuronide levels: Urine samples will be obtained at intake to confirm the menthol preference of smokers (Benowitz *et al*, 2010). Additional urine samples will be collected throughout each test session to measure the amount of menthol exposure (via urinary menthol glucuronide levels) that was provided by the e-cigarette.
- Plasma menthol glucuronide levels: Blood samples will be obtained throughout each test session to determine the amount of menthol delivered by the e-cigarette. Blood samples will be obtained prior to each of the three experimental vaping sessions, and at 2 time points after each nicotine or saline infusion. An additional blood sample will be obtained just prior to removing the IV. Plasma levels of menthol glucuronide will be measured at different time points to generate concentration-time curves for each menthol delivery. This will help characterize the pharmacokinetics of menthol and account for differing menthol exposure between subjects.

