- Alveolar carbon monoxide: CO readings $\leq 10\text{ppm}$ will be used to verify overnight abstinence from smoking as recommended by the SRNT Subcommittee on Biochemical Verification (Benowitz *et al*, 2002).

c) Subjective:

- Measures of Dependence:
 - 1) DSM-IV Nicotine Dependence Questionnaire.
 - 2) Structured Clinical Interview for DSM-IV (SCID) for Axis I disorders: SCID is a semi-structured interview based on DSM-IV (American Psychiatric Association, 1994) and will be performed to diagnose Axis I psychiatric disorders.
 - 3) Fagerstrom Test of Nicotine Dependence (FTND): This self-report measure assesses the degree of nicotine dependence and has been used widely in smoking studies (Heatherton *et al*, 1991).
- Measures of withdrawal and negative affect:
 - 1) Minnesota Nicotine Withdrawal Symptom Checklist (M-NWSC): Smokers will be asked to rate several nicotine withdrawal symptoms on a 100 mm scale, from 'not at all' to 'extremely'. The items are derived from the M-NWSC (Hughes and Hatsukami, 1986) and have been used in previous human laboratory studies (Eissenberg *et al*, 1996). The items include cigarette craving, irritability/anger, anxiety/tension, difficulty concentrating, restlessness, increased appetite, depressed mood, and insomnia.
 - 2) Positive and Negative Affect Schedule (PANAS): The PANAS is a 20-item scale that assesses both negative and positive affective states (Watson *et al*, 1988). This scale is sensitive to the affective symptoms of tobacco withdrawal and predicts relapse to smoking (Kenford *et al*, 2002).
 - 3) Brief Questionnaire on Smoking Urges (BQSU): This 10-item scale, originally developed by Tiffany and Drobes (Tiffany and Drobes, 1991), has been found to be highly reliable and

[Type text]

[Type text]

reflects levels of nicotine deprivation (Bell *et al*, 1999; Morgan *et al*, 1999). This scale will be used to monitor cigarette craving.

- 4) Center for Epidemiologic Studies Depression (CES-D) scale: The CES-D is a 20-item self-report measure of depressive symptoms (Radloff, 1977). This scale will be used at intake to control for baseline differences in depressive symptoms.
- 5) E-cigarette Questionnaire: This 10 item self-report questionnaire was developed by our research group to characterize the study populations' experience with, and attitude about, e-cigarettes. This questionnaire will be administered during the Adaptation Session.

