- Subjective Drug Effects: 1) Drug Effects Questionnaire (DEQ), adapted from Soria (1996), will be used during the test session to measure acute drug responses including: liking, cooling, irritation, strength, feeling, stimulation, good effects, bad effects, head rush, and want more. Each item is rated on a 100 mm scale, from 'not at all' to 'extremely'.
- Drug Use: Self-reports of cigarette smoking and use of other tobacco products, alcohol and drugs (cocaine, alcohol, opioids, marijuana, and other illicit drugs) will be assessed with Time Line Follow-Back, which has been shown to be a reliable and valid method for monitoring substance use and other outcomes in longitudinal studies (Miller and DelBoca, 1994; Sobell and Sobell, 1992). The Time Line Follow-Back will be administered at intake.
- Adverse events: SAFTEE: In order to monitor adverse events from the study medications, the SAFTEE will be administered before and after each session. The SAFTEE has been used in a number of pharmacotherapy trials (Levine and Schooler, 1986).
- Cognitive Performance: Cognitive performance will be assessed with 3 tests from the ANAM battery (University of Oklahoma): the Stroop test, the mathematical processing test (MPT), and the continuous performance test (CPT). These 3 tests were chosen because of their sensitivity to tobacco withdrawal and nicotine administration (Heishman *et al*, 2010; Mancuso *et al*, 1999; Myers *et al*, 2008).
 - Stroop Test: This test assesses processing speed, selective attention, and interference (Spreen, 1991). It is a computerized version of the classical Stroop Test (Reeves, 2002). The Stroop design consists of one three-minute block of congruent stimuli, and one three-minute block of incongruent stimuli.
 - Mathematical Processing Test (MPT): This test assesses basic computational skills, concentration, and working memory. An arithmetic problem involving three single-digit numbers and two operators is displayed (e.g., "5 - 2 + 3 ="). The subject presses buttons to indicate whether the answer to the problem is less than five or greater than five.
 - Continuous Performance Test (CPT): This test assesses sustained attention, concentration, and working memory. A target character is displayed for memorization. Then, as individual characters are displayed in sequence, the user presses a designated button only when the displayed character is the target letter.

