For 24 hours prior to each Test Session, subjects will be asked to avoid using products containing menthol such as mint teas, cough lozenges, and mint-flavored gum. If needed, a trial-size tube of toothpaste that does not contain menthol will be provided for use the morning of each Test Session. Subjects will be required to abstain from smoking for 10 hours. Abstinence will be verified by expired air CO levels \leq 10 ppm (Benowitz et al. 2002) measured on the morning of testing. Subjects will also be asked to refrain from consuming alcoholic beverages and drugs during study participation. Abstinence will be verified by urine drug screening and Breathalyzer measurements before the test sessions. If results indicate non-compliance with these study procedures, the session will be rescheduled. Repeatedly non-compliant subjects will be discharged from the study. Subjects will be instructed to drink their typical amount of caffeinated beverages in the morning to minimize caffeine withdrawal, which could confound interpretation of study measures. Subjects will be given a light breakfast before each test session and a lunch will be provided at the end of each test session.

[Type text]
[Type text]

- a) Adaptation Session: This session will take place at the West Haven VA prior to the nicotine Test Sessions. The goal of the Adaptation Session is to familiarize participants with the study procedures including the use of e-cigarettes, and to gather information regarding participants' use and knowledge about e-cigarettes. Participants will be given an e-cigarette and instructed to inhale more softly, but for a longer duration (3-4 seconds), than is customary for a standard cigarette. Additionally, a two-phase inhalation is suggested where the vapor from this elongated inhalation is initially gathered in the mouth (as one might do with pipe tobacco) but then further inhaled into the lungs. The e-cigarette used in this Adaptation Session will not contain nicotine, or menthol, only the control flavor (tobacco) mixed with the base liquid. Although the familiarization with this technique will occur during the Adaptation Session, participants will be reminded of this technique during each test session prior to the e-cigarette administration. In total, the e-cigarette vaping procedure consists of 6 inhalations at a rate of one inhalation every 15 seconds.

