- b) Test Sessions: Experimental sessions will start around 8:30 AM. As summarized in Table 2, baseline biochemical measures will include urine menthol glucuronide and cotinine, plasma nicotine, and for women, estradiol and progesterone levels. These samples will be obtained followed by cognitive testing. Subjects will then start inhaling from the e-cigarette with the assigned menthol condition (control flavor, low or high dose of menthol), one inhalation every 15 seconds as practiced in the adaptation session. It will take approximately 90 seconds to complete 6 inhalations. Subjects will then receive the first delivery of the assigned injection (saline, 0.25 mg/70 kg or 0.5 mg/70 kg nicotine). Each study injection will be 60 minutes apart to provide sufficient time for the physiological and subjective nicotine effects to return to baseline. Following each injection, physiological, subjective, and cognitive outcome measures will be obtained.
- c) Medical monitoring: For nicotine test sessions, a physician will be present and subjects will be attached to a blood pressure and heart rate monitoring device. An IV catheter will be in place throughout the session. Subjects will be administered nicotine only if the systolic blood pressure is <150 mmHg and heart rate is <100 beats/minute. Subjects will be terminated from the study if the blood pressure at any time is >170/110 mm Hg, the heart rate is >120 beats/min, or if they develop signs and symptoms compatible with nicotine toxicity. Subjects

[Type text]

[Type text]

will remain in the laboratory for three hours after the last nicotine administration. These procedures have been developed as part of our IND application for IV nicotine.

Table 2. Schedule of Events: Experimental Session*

Time	Measures and Events
8:00 AM	(Building 36) CO level, urine sample, BAL, and light standard breakfast
9:00 AM	(Biostudies Unit) blood sample. HR/BP, EKG, M-NWSC, BQSU, SAFTEE, Cognitive Testing
11:00 AM	Menthol (control, high or low Menthol) DEQ + IV Saline or Nicotine (0.25 or 0.5mg/70 kg) blood draw
11:01	HR/BP, DEQ
11:02	HR/BP
11:03	HR/BP, DEQ,
11:05	HR/BP, DEQ
11:08	HR/BP, DEQ blood draw
11:10	HR/BP, DEQ
11:15	HR/BP, DEQ, Cognitive Testing
11:30	HR/BP, DEQ blood draw
11:45	HR/BP, DEQ
11:55	HR/BP, DEQ, BQSU
12:00	Menthol (control, high or low Menthol) DEQ + IV Saline or Nicotine (0.25 or 0.5 mg/70 kg), blood draw
13:00	Menthol (control, high or low Menthol) DEQ + IV Saline or Nicotine (0.25 or 0.5 mg/70 kg), blood draw

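### Test Sessions are meant to follow abstinence from tobacco, but the working rule and its only same-day check cover smoking alone, so non-combusted nicotine can pass

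*Protocol*

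**What the plan says.** - **Intended state.** Protocol section 11.A (Overview): "the nicotine Test Sessions will be performed following overnight abstinence from tobacco".
- **Instruction to subjects.** Study Procedures: "Subjects will be required to abstain from smoking for 10 hours". Section 13 (item 6, study procedures) likewise describes the abstinence period as one in which subjects cannot smoke.
- **Check.** Study Procedures: "Abstinence will be verified by expired air CO levels" at or below 10 ppm on the morning of testing. Section 11.D (Biochemical) gives the purpose of CO: it "will be used to verify overnight abstinence from smoking as recommended by the SRNT Subcommittee on Biochemical Verification". Non-compliance leads to rescheduling. The urine drug screen and Breathalyzer are tied to drugs and alcohol.
- **Nicotine assay.** Section 11.D has plasma nicotine taken "prior to the first experimental vaping session on each test day to characterize the subject's smoking status". Study Procedures, Test Sessions, lists it among the baseline measures: "baseline biochemical measures will include urine menthol glucuronide and cotinine, plasma nicotine". Neither place gives a limit or an action.
- **Other products.** The Time Line Follow-Back records "Self-reports of cigarette smoking and use of other tobacco products", at intake only. The e-cigarette questionnaire is given at the Adaptation Session. The criteria in section 7 exclude neither e-cigarette nor smokeless tobacco users.

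**The concern.** The design gives small intravenous nicotine doses to smokers who are meant to be nicotine-deprived. A subject who used a non-menthol nicotine e-cigarette early on a test day would breach the Overview's statement of intent at most. That subject would break no working instruction and would pass the CO gate.

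The exposure is foreseeable from the Protocol itself. It asks about other tobacco products and e-cigarette experience, and its background and risk sections mention mentholated chewing tobacco and menthol e-cigarettes.

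Menthol condition changes between days while nicotine dose varies within a day. The nicotine-by-menthol interaction that tests Hypothesis 1A therefore compares nicotine responses across days. Each subject has one session per menthol condition, so a lapse on one day and not another enters that comparison directly.

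**Working it through.** The Protocol states no figure to reproduce. The check sets the passages side by side and then traces where undetected nicotine would enter the analysis.

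**Step 1: definition against check**

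| Place | Scope | Can it reschedule a session? |
|---|---|---|
| 11.A Overview | tobacco | states intent only |
| Study Procedures, 10-hour rule | smoking | yes, through CO |
| 11.D, CO | smoking | yes, same gate |
| 13, item 6 | smoking | no |
| 11.D and Test Sessions, plasma nicotine | nicotine from any source | no limit or action stated |
| Test Sessions, urine cotinine | baseline measure | no abstinence criterion |
| Time Line Follow-Back | other tobacco products | no, intake only |

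CO is a marker of combustion, and the Protocol claims no more for it than abstinence from smoking. The gate therefore verifies the narrower rule, not the state that the Overview describes.

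**Step 2: effect on Hypothesis 1A**

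Let the nicotine-minus-saline response in a session be N with control flavor and N + E with menthol. Let p be the share of sessions preceded by recent nicotine and *a* the proportion by which it blunts the response. Neither p nor *a* is in the documents. The menthol sequence is randomized, so p is taken as equal across conditions.

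- If only N is blunted: [N(1 − ap) + E] − N(1 − ap) = E. The interaction is unbiased on average. For one subject, however, a lapse on the menthol day alone shifts it by −aN, and a lapse on the control day alone by +aN. This is noise.
- If the whole response is blunted: (N + E)(1 − ap) − N(1 − ap) = E(1 − ap). The interaction is attenuated.

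**Step 3: effect on Hypothesis 1B**

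Section 12 tests 1B by the nicotine-by-menthol-by-group interaction. Let strata 1 and 2 have lapse shares p₁ and p₂ and enhancements E₁ and E₂.

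- If only N is blunted, the contrast is E₁ − E₂, with no bias even when p₁ ≠ p₂.
- If the whole response is blunted, it is E₁(1 − ap₁) − E₂(1 − ap₂). With E₁ = E₂ = E this equals aE(p₂ − p₁). It is zero unless lapses differ by stratum and E is not zero.

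**Step 4: what a covariate can do**

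Let x be the session's pre-vaping plasma nicotine. A main-effect term βx is added equally to the saline and nicotine records of that session, so it cancels: βx − βx = 0. With an interaction with nicotine dose, (β_nicotine − β_saline)x remains, and only this term can adjust the contrast of interest.

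**The case against.** The strongest points on the other side are these.

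- **Some products are already barred.** The Overview says tobacco, which covers smokeless products. The 24-hour request to avoid menthol products, as worded, would cover mentholated e-cigarettes. Both points stand and narrow the gap. But the menthol rule's examples are teas, lozenges and gum, and no same-day gate is tied to it.
- **CO at 10 ppm has a cited basis.** It does, for abstinence from smoking. That does not extend it to non-combusted nicotine.
- **Timing.** The CO check is at 8:00 and the first infusion at 11:00, and the Protocol regards 60 minutes as enough for nicotine effects to return to baseline. This weakens any claim of acute carry-over from early-morning use. It does not dispose of the point, because the Protocol's own 10-hour rule asks for deprivation well beyond a one-hour washout.
- **Recent nicotine is not wholly undetected.** The plasma assay could reveal it later. This stands: the gap is in the same-day gate and in the lack of an assigned use for the assay.
- **Covariates and sensitivity analyses belong in an SAP.** Agreed, and their absence from the Protocol is not part of this point. What subjects are told to avoid, and what verifies it, are matters of protocol conduct.

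A reader might also infer a sizeable bias in 1B. For example, assuming 10–30% of sessions affected and 30–50% blunting gives 0.10 × 0.30 = 3% to 0.30 × 0.50 = 15%, which might be read as a spurious group difference. The documents support neither input. The product also describes the nicotine response by group, not the three-way term that tests 1B.

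**Conclusion.** The mismatch is real. Sections 11.D and 13 and Study Procedures require and verify abstinence from smoking, while the Overview calls for abstinence from tobacco. Nicotine from non-combusted products can pass the only gate, and the assay that could show it has no stated role in checking abstinence.

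The expected harm is added between-session noise and attenuation of the nicotine response in the nicotine-by-menthol contrast. Its size cannot be estimated, because the documents give neither a rate of dual use nor a degree of blunting. The finding that 1A is not systematically tilted rests on the randomized menthol order and on lapses being unrelated to the assigned condition. Menthol preference is not randomized, so bias in 1B cannot be ruled out. It needs both unequal recent use between strata and blunting that scales menthol's enhancement, and the documents show neither. The point is of moderate weight and worth acting on chiefly because the remedy is nearly free.

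**What to change.** 1. Reconcile section 11.A, section 11.D, Study Procedures and section 13 (item 6) to one definition of abstinence that names all tobacco and nicotine products, including e-cigarettes and smokeless tobacco. Keep CO as the same-day gate.
2. State in section 11.D that each session's plasma nicotine, "measured from blood that was obtained prior to the first experimental vaping session on each test day", is the retrospective abstinence check.
3. In section 12 or the SAP, add a sensitivity analysis of the primary model that excludes sessions above a limit fixed before unblinding. The sample precedes that day's vaping and infusions, so the exclusion does not depend on that session's response.
4. If plasma nicotine is used as a covariate, include its interaction with nicotine dose, since a main effect alone cancels.

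The cost is a few sentences. No visit, sample or assay is added. A few sessions drop out of the sensitivity analysis, but the mixed model still uses those subjects' other sessions. The instruction has to be in place before sessions are run, because analysis can flag affected sessions later but cannot restore them.

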14:00 noon	HR/BP, EKG, M-NWSC, BQSU, SAFTEE

[Type text]

[Type text]

15:00 PM	End of session, collection of urine sample, blood draw Discharge
----------	---

*The same measures will be obtained following saline and each nicotine administration. For brevity, only the measures after saline are shown. Abbreviations: CO: Alveolar carbon monoxide; HR/BP: Heart rate/Blood pressure; EKG: Electrocardiogram; M-NWSC: Minnesota Nicotine Withdrawal Symptom Checklist; BQSU: Brief Questionnaire of Smoking Urges; DEQ: Drug Effects Questionnaire; SAFTEE: Systematic Assessment for Treatment Emergent Events.

12. Data analysis methods

Data analyses: The primary analyses will be intent-to-treat and will include all available data on subjects who complete at least one test day. Mixed-effects models will be used to test the study hypotheses. These models allow for different numbers of observations per subject, use all available data on each subject, and are unaffected by randomly missing data. They also provide flexibility in modeling the correlation structure of the data. All data will be checked for normality and transformations will be applied as necessary. Significance level of 0.05 will be used for the main hypotheses and Bonferroni correction will be applied for post-hoc tests.

Specific Aim #1: To determine if menthol administered via e-cigarettes will change the reinforcing effects of pure nicotine administered intravenously in cigarette smokers who smoke mentholated or non-mentholated cigarettes. The reinforcing drug effects will be measured with the DEQ.

Hypothesis #1A: Concurrent menthol and nicotine administration will lead to greater reinforcement than nicotine and control flavor, saline and menthol, or saline and control flavor conditions.

Hypothesis #1B: Enhancement of nicotine reinforcement by menthol will be greater in menthol smokers than in non-menthol cigarette smokers.

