Potential risks:

There are potential risks, discomforts and inconveniences associated with participation in this study. These may be due to nicotine or menthol administration, blood drawing, other study procedures and potential loss of confidentiality.

1) Common side effects of nicotine include nausea, vomiting, heartburn, and elevated heart rate and blood pressure. Toxic doses of nicotine may cause abdominal pain, hyper salivation, diarrhea, dizziness, confusion, hearing and vision problems, syncope, seizures, hypotension, irregular pulse, and death. However, these toxic effects occur at doses 40 to 50 times that which will be used in our study. Other potential risks from this study include administering a drug that has addictive potential.

2) Menthol administration produces typical sensory effects in the mouth and throat. The doses of menthol that are found in cough drops, ranging 1 to 10 mg are regarded to be safe (Sweetman, 2011). In spite of ubiquitous use of menthol in a wide range of products, only few cases of menthol poisoning has been described in the literature following very high doses of menthol ingestion, 200 mg or more. Menthol poisoning reported to cause ataxia, confusion, coma, nausea, and vomiting. However, these toxic effects occur at doses 20 to 30 times that which will be used in our study.

3) The combination of intravenous nicotine and inhaled menthol has not been previously examined to the best of our knowledge. We have no reason to believe there is an increased risk from the combination used in this study as compared to the widespread use of mentholated cigarettes, menthol e-cigarettes or smoking while using a menthol-containing lozenge. However, the administrations will be closely monitored for any signs that this unique combination of IV nicotine and inhaled menthol results in unexpected findings.

4) Propylene glycol and vegetable glycerin are categorized by the FDA as compounds that are Generally Recognized As Safe (GRAS). They are both commonly used ingredients in food products, pharmaceuticals and in personal care products. They are also now used as the base liquid ingredient for e-cigarettes. Although e-cigarettes are reported to be helpful for smoking cessation, the FDA has not approved e-cigarettes for this use, and the long-term consequences of e-cigarette use have not been assessed.

[Type text]

[Type text]

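### The SAFTEE is given once after all three infusions, so symptoms recorded only there cannot be compared between nicotine and saline or for the menthol-nicotine combination

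*Protocol*

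**What the plan says.** Section 11.D (Measures, c) Subjective) names one adverse event instrument: "In order to monitor adverse events from the study medications, the SAFTEE will be administered before and after each session". Table 2 agrees. The pre-dosing row at 9:00 reads "HR/BP, EKG, M-NWSC, BQSU, SAFTEE, Cognitive Testing" and the row at 14:00 reads "HR/BP, EKG, M-NWSC, BQSU, SAFTEE". The three infusions fall between them, at 11:00, 12:00 and 13:00.

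Section 11.A (Overview) fixes what each session contains: "In each Test Session, smokers will receive a random order of one intravenous delivery of saline, and two intravenous deliveries of nicotine". The menthol condition is constant within a day, with "a different menthol condition for each session". On spacing it says: "The intravenous dose deliveries will be one hour apart to provide sufficient time for the nicotine and menthol effects to wear off".

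The Table 2 footnote repeats the post-infusion measures after saline and after each nicotine dose. The block that it repeats (11:01 to 11:55) holds heart rate, blood pressure, DEQ, blood draws, cognitive testing and BQSU. The SAFTEE is not in it.

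Section 13 (Potential risks, item 3) notes that intravenous nicotine with inhaled menthol has not, to the investigators' knowledge, been studied before, and says that "the administrations will be closely monitored for any signs that this unique combination of IV nicotine and inhaled menthol results in unexpected findings". Under Protection of Subjects, the same section names the expected nicotine events: nausea, vomiting, heartburn, and raised heart rate and blood pressure.

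**The concern.** Saline is randomised within each session so that nicotine effects can be judged against it. The SAFTEE makes no use of that control. In a completed session its single post-dosing reading always follows saline, the low nicotine dose and the high nicotine dose together. Only the menthol condition differs from one reading to the next.

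Nausea, vomiting and heartburn are three of the five expected nicotine events, and none of them is a DEQ item. If a subject mentions one of them only when asked at 14:00, the record does not show which infusion it followed. An excess in menthol sessions could come from menthol alone or from menthol with nicotine. The second is what Section 13 says will be watched.

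**Working it through.** The protocol gives no figure to reproduce. The check is which comparisons the schedule can support.

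**Inputs.** Three menthol conditions, one per session (Section 11.A). Three infusions per session: saline, 0.25 and 0.5 mg/70 kg (Section 11.A, Table 2). One post-dosing SAFTEE at 14:00 (Table 2). No onset time or infusion number is required for a SAFTEE event.

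**Step 1: recall interval.** The 14:00 reading comes 3 hours after the first infusion, 2 after the second and 1 after the third.

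**Step 2: contrasts available.** There are 3 × 3 = 9 conditions and so 8 contrasts: 2 for menthol, 2 for nicotine and 2 × 2 = 4 for their interaction. Treat the SAFTEE as one undated reading per session that pools its three infusions. Each subject then gives three readings, one per menthol condition.

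| Comparison | SAFTEE at 14:00 only | Recorded after each infusion |
|---|---|---|
| Rank of the design (of 9) | 3 | 9 |
| Low or high menthol session vs control-flavor session | estimable | estimable |
| 0.25 or 0.5 mg/70 kg vs saline | not estimable | estimable |
| High menthol + 0.5 vs control flavor + 0.5 | not estimable | estimable |
| Menthol × nicotine interaction | not estimable | estimable |

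Rank 3 is the overall mean plus the 2 menthol contrasts. The 2 nicotine and 4 interaction contrasts are lost.

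**Step 3: illustration.** The event risks here are assumptions, not protocol figures, and the infusions are taken as independent. The chance of at least one event in a session is 1 − (1 − p_saline)(1 − p_low)(1 − p_high).

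- Control-flavor session with risks of 2%, 5% and 10%: 1 − 0.98 × 0.95 × 0.90 = 16.2%.
- Menthol acts only with the high dose (10% to 20%): 1 − 0.98 × 0.95 × 0.80 = 25.5%.
- Menthol acts only with saline: the same session figure needs p_saline = 1 − 0.7448/(0.95 × 0.90) = 12.9%, and again gives 25.5%.
- Menthol acts only with the low dose: p_low = 1 − 0.7448/(0.98 × 0.90) = 15.6%, and again 25.5%.

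The pattern does not depend on the chosen risks. The session figure depends only on the product of three terms, so one reading cannot show which term changed.

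**Step 4: what is recorded by infusion.** Table 2 lists heart rate and blood pressure at ten times after an infusion (+1, +2, +3, +5, +8, +10, +15, +30, +45, +55 minutes) and the DEQ at nine (the same times without +2). Two of the five expected nicotine events, raised heart rate and raised blood pressure, therefore do have a saline control. So do the DEQ items on bad effects, irritation and head rush.

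**The case against.** A reader might infer that no adverse event in this trial can be assigned to an infusion. The document does not support that. Heart rate, blood pressure and the DEQ are taken after every infusion. A physician watches throughout, the infusions are an hour apart, and the investigator reviews and attributes every event. Vomiting seen minutes after an infusion can be tied to it. All of this stands.

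A reader might also infer that no sample size could ever recover the lost contrasts. That holds only if the reading is undated and pools the three infusions. Nicotine may be withheld on the blood pressure or heart rate criteria, and participation can end mid-session, so some sessions will be incomplete and carry partial information. If the SAFTEE captures how the subject feels at 14:00, the randomised 13:00 infusion carries information too.

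On paperwork, Section 13 says that parameters for collecting side effects will be put to the DSMB before the study starts. Onset time is a case-report-form field, and a table by condition belongs in an analysis plan. Neither document is at hand, so their absence here is no fault. The timing of the SAFTEE, however, is set in the protocol. An analysis plan cannot restore infusion-level symptoms that were never recorded.

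Finally, adverse events are not a hypothesis or a listed outcome. The promise to monitor the combination can be read as bedside observation, and no nicotine-versus-saline event rate is promised. The assumed 16.2% control-session risk also sits awkwardly beside the protocol's report of more than 400 smokers given intravenous nicotine with no adverse event attributed to it. These points lower the weight of the matter. They do not change what the schedule can separate.

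**Conclusion.** The point holds for symptoms that enter the record only through the SAFTEE. As scheduled, they support a comparison of menthol with control-flavor sessions. They do not support nicotine against saline, one nicotine dose against the other, or menthol plus nicotine against menthol plus saline. Under the pooled, undated reading, 2 of 8 contrasts are available. This assumes completed sessions and no infusion link on the form.

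The text in Section 11.D and Table 2 agree with each other, so this is no contradiction. It is a gap in tolerability data that is cheap to close before data collection and hard to close afterwards. The primary DEQ analysis is unaffected.

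**What to change.** At the existing +55 minute reading after each infusion, once the DEQ and BQSU are done, ask about the symptoms that the protocol lists for nicotine and menthol. Record onset time and infusion number (1, 2 or 3) for each event; this does not reveal the dose, so the blind is kept. Keep the 9:00 and 14:00 SAFTEE. After unblinding, tabulate events within subject by the nine menthol-by-nicotine conditions, beside the DEQ bad effects and irritation items. The references for the combination are menthol plus saline and control flavor plus nicotine.

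The cost is a few minutes per infusion, a form field and one table, with no added staff or visits. Repeated asking may slightly raise reports of mild symptoms, but equally across the randomised infusions. No dose, stopping rule or clinical management changes.
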